3.4 Additional Outcomes

Additional outcomes have been included due to a) interest from the study team and b) to reflect those intermediate outcomes in the Pregnancy Circles logic model which are not included as secondary outcomes (see Wiggins et al., 2020). Additional outcomes have been listed separately from secondary outcomes to avoid multiplicity issues due to an excessive number of secondary outcomes and are to serve predominantly for hypothesis generation.

- 1. Social support using Duke Social Support Scale (continuous: scores range from 8-40, higher scores favoured)
- Self-efficacy using Perlin Mastery Scale (continuous: scores range from 7-28 with higher scores favoured)
- 3. Prenatal stress using Revised Prenatal Distress Questionnaire (continuous: 12-item total score, scores range from 0-16; higher is favoured)
- 4. Health literacy using Health Literacy Questionnaire (continuous: score on only first domain of HLQ, range 1-20, higher score favoured)
- 5. Attendance at antenatal care (continuous: number of sessions, higher is favoured)
- 6. Additional measures of satisfaction with care (categorical: (FU1) Overall, how do you feel about the care you received from midwives? Options very happy, fairly happy, not very happy, very unhappy; (FU2) Overall, how do you feel about the care you received from midwives (before the birth of your baby)? options very happy, fairly happy, not very happy, very unhappy)
- 7. Caesarean delivery (categorical: planned, emergency, none)
- 8. Infant birth weight in grams (continuous)
- 9. Place of birth (categorical: actual place of delivery; options= hospital obstetric unit, hospital alongside midwifery unit, freestanding midwifery unit, home or other)

- 10. Breast feeding continuation and exclusivity (binary: did mother exclusively breastfeed to 3-month follow-up, yes favoured --> however will look at exclusive, breast milk, artificial exclusive, mixed, other in descriptive analysis)
- 11. Postnatal depression using Edinburgh Postnatal Depression Scale (binary: mothers scoring above 13 are "likely to be suffering from a depressive illness of varying severity", no favoured)

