- 12. Postnatal symptoms using NPEU (National Perinatal Epidemiology Unit) checklist (based on the NPEU checklist items to produce a single score variable; continuous; lower scores favoured from 0 to 5). The items include psychological symptoms (e.g. "the blues", depression, anxiety); posttraumatic stress-type symptoms (e.g. flash-backs, difficulties concentrating, sleep problems not related to the baby); bodily changes (e.g. stress incontinence, backache; difficulties/pain during intercourse); birth-related symptoms (e.g. painful stitches, wound infection); breastfeeding problems and severe fatigue.
- 13. Immunisation (categorical: Has your new baby had their routine immunisations at 2 months and 3 months of age? Options yes 2 months; no 2 months; yes 3 months; no 3 months)
- 14. Continuity of antenatal care (categorical: how many midwives did you have during care; options=1-2, 3, 4+ or don't know with 1-2 being favoured) and satisfaction with continuity (categorical: Do you feel in general that the midwives you saw during your regular antenatal appointments got to know you and remembered you and your progress? Options yes definitely; yes, a little; no, not really; no, not at all; don't know can't remember; How satisfied are you with how much midwives got to know you and remember you and your progress? Options very satisfied; quite satisfied; not at all satisfied; don't know/can't remember; Do you feel that midwives have been sensitive to your cultural and/or language needs? Options yes, definitely; yes, a little; no, not at all; don't know/can't remember)
- 15. Choice in care (categorical: Were you offered any of the following choices about where to have your baby? Options a choice of different hospitals; in a midwife-led unit or a birth centre; in a consultant-led unit; at home; I was not offered any choices; I was not offered any choices due to medical reasons; don't know)
- 16. Involvement in care (categorical: Thinking about your regular antenatal care, do you think you were involved enough in decisions about your care? Options yes, always; yes sometimes; no and I wanted to be; no and I did not want to be; don't know)
- 17. Preparedness for labour and birth (categorical: How prepared did you feel for labour and birth? options: very well, quite well, not very well and not at all well and How well did you manage during labour? options very well, quite well, not very well and not at all well)

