5.5 General analysis principles

The analysis of primary, secondary, and, where possible, additional outcomes will be adjusted for the stratification factors which were used during randomisation, centre, and ability to speak English, only. All main analyses will be performed on a complete case basis (ignoring missing data) for the outcomes in question. A missing category will be created for the only covariate in the models "ability to speak English". The significance for statistical tests (alpha) will be 5%, all confidence intervals will be presented at the 95% level and all p-values will be two-sided. As the intervention arm includes group pregnancy circles, clustering will be accounted for in the intervention arm using pregnancy

circles as the units of clustering, while participants in the control arm will be modelled as a cluster size of one [1].

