Secondary and additional outcomes providing continuous responses, such as a total score on any of the scales being used, will be analysed by assessing difference of means between intervention and control groups. This will be analysed using a partially nested mixed-effects model with heteroskedastic error terms with the Satterthwaite approximation for degrees of freedom to avoid upward bias of the type-I error rate (2). The English level will again be included as covariate in these models. The resulting model will estimate a difference of means between the intervention and control arms of the study. Specifically, let y be the continuous outcome, i is the mother participant indicator, j is the pregnancy indicator, t is the intervention indicator (0 = usual care, 1 = pregnancy circle), θ is the intervention effect, θ_0 is an intercept term, and θ_k represents fixed effects for English level. Then,

$$y_{ij} = \beta_0 + \theta t_{ij} + \beta_k + u_i t_{ij} + r_{ii} (1 - t_{ij}) + \epsilon_{ij} t_{ij} + v_1$$

where $u_j \sim N(0, \sigma^2_u)$ is a random-effects term representing between-cluster (pregnancy circle) variation in the clustered intervention arm, $r_{ij} \sim N(0, \sigma^2_r)$ represents individual-level variation in the

non-clustered control arm, $\epsilon_{ij} \sim N(0, \sigma^2_{\epsilon})$ represents individual-level variation in the clustered intervention arm and $v_i \sim N(0, \sigma^2_w)$ is the random effect representing between-site variation.

Analysis of categorical outcomes

For categorical outcomes, proportions by intervention group and test of between group difference without covariate adjustment will be presented.

Strategy for analysis of primary outcome if model fails to converge

In case the analysis of the primary outcome described above fails to converge, the following sequential strategy will be employed (starting at 1).

	Change from previous strategy
1	Try an alternative estimation algorithm, such as the
	QR decomposition in meqrlogit, rather than Stata's
	default melogit function.
2	Change the number of integration (quadrature)
	points for all levels using intpoints() command
3	Try an alternative integration method other than
	mean-variance adaptive Gauss-Hermite
	quadrature like Laplace for example.
4	Remove covariate English speaking level from the
	model.
5	Analysis using model, not assounting for clustering
5	Analyse using model, not accounting for clustering
	within intervention groups.

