A logistic regression model will be used for missing values of binary variables and a multinomial logistic regression model will be selected for missing values of categorical variables with three or more unordered categories. Missing values of categorical variables with three or more ordered categories will be modelled using ordinal logistic regression and a linear regression model will be specified for continuous variables with missing data. Auxiliary variables – that is, variables that are not included in the intended analysis of imputed variables but are the highly correlated with the imputed variables (or its missingness) – will be included in the imputation model (6).

Next, an 'estimation' step will be conducted, whereby specified analyses – as described in sections 5.7 – will be performed separately for each completed dataset that is generated during the imputation step. Finally, a 'pooling' step will be performed, whereby point estimates (e.g., sample means) and measures of precision (e.g., standard deviations) estimated in each dataset will be aggregated using Rubin's Rules to create a final estimate that accounts for between- and within-imputation uncertainty (7).

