Primary outcome is in bold and underlined and secondary outcomes are in bold and italic

^{*} PC for Pregnancy Circle group

^{**} ICC for clustering in intervention group (cluster is PC group)

^{***} Confidence interval is established using Swiger's method

Table 3: Results of secondary and additional continuous outcomes at 35 weeks and 3 months post-partum

	Number in	cluded in	Summary	measure	Treatment	effect		
	analy	/sis	-					
Outcome	Usual care	PC	Usual care	PC	Mean	(95% CI)	p-value	ICC**
	n (%)	n (%)	Mean (SD)	Mean (SD)	difference			[95 % CI]***
Pregnancy-								
related								
Empowerment								
Scale (PRES)								
Range 16-64								
Week 35								
Friends and								
family test								
Range 1-5								
Week 35								
Month 3 pp								
Emotional								
Wellbeing								
(SWEMWBS)Ra								
nge 7-35								
Week 35								
The Duke-UNC								
Functional								
Social Support								
Questionnaire								
Range 8-40								
Month 3 pp								
Pearlin								
Mastery Scale								
Range 7-28								
Month 3 pp								
Revised								
prenatal								
distress scale								
Range 0-16								
Week 35								
Infant birth								
weight (g)								
Month 3 pp								
Health literacy								
Range 1-20								
Week 35								

Post natal				
symptoms				
(NPEU)				
Range 0-5				
Month 3 pp				
Number of				
antenatal care				
sessions				
attended				

Secondary outcomes are in bold and italic

Table 4: Analysis of categorical Additional Outcomes

	Number include	ed in analysis	Summary	measure	
Outcome	Usual care n (%)	PC n (%)	Usual care %	PC %	P value for between group difference
How do you feel about the care you received					
from midwives? (week 35)					
very happy					
fairly happy					
not very happy					
very unhappy					
Missing					
How do you feel about the care you received					
from midwives (before the birth of your					
baby)? (3 months pp)					
very happy					
fairly happy					
not very happy					
very unhappy					
Missing					
Caesarean delivery					
Planned					
Emergency					
None					
Missing					
Place of birth					
Hospital obstetric unit					
Hospital alongside midwifery unit					
Freestanding midwifery unit					
Home					
Other					
Missing					

^{*}PC is for Pregnancy Circle group

^{**} ICC for clustering in intervention group (cluster is PC group)

^{***} Confidence interval is established using Swiger's method

Has your new baby had their routine		
immunisations?		
Yes 2 months		
No 2 months		
Yes 3 months		

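### The ordered additional outcomes get only percentages and a p-value from an unnamed test: no use of the order, no effect with an interval, no stated handling of clustering or of don't-know answers

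*SAP*

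**What the plan says.** Section 5.9 gives one sentence to the categorical outcomes: "For categorical outcomes, proportions by intervention group and test of between group difference without covariate adjustment will be presented". No test is named. Dummy Table 4 (section 8.4) has the number analysed and the percentage per arm, and one further column, "P value for between group difference". It has no column for an effect estimate or interval.

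The outcomes under this rule are mixed. Some are nominal, such as place of birth. Others are ordered scales in section 3.4, for example satisfaction with midwife care, "Options very happy, fairly happy, not very happy, very unhappy", and preparedness for labour, "options: very well, quite well, not very well and not at all well". For number of midwives, section 3.4 even states which end is favoured.

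Other parts of the SAP bear on the same outcomes:

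- Section 5.5 adjusts additional outcomes for the stratification factors where possible. It also says that clustering by Pregnancy Circle will be accounted for in the intervention arm, and that "all p-values will be two-sided".
- The fallback table in section 5.9 collapses categories if a categorical outcome has convergence problems, although no model is specified for these outcomes.
- Section 3.4 says that additional outcomes serve mainly to generate hypotheses.

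**The concern.** A single rule covers items with and without a natural order. For an ordered scale the natural question is whether answers shift towards the better end, by how much and with what uncertainty. A table of percentages with one p-value leaves the size of the shift unsummarised and its precision unstated.

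Binary outcomes get an odds ratio and risk difference with intervals (Table 2), and continuous ones a mean difference with an interval (Table 3). Even the single 1-5 Friends and Family item is modelled on its ordered score. The four-level satisfaction items get neither estimate nor interval.

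Two further gaps follow from the same sentence. It is silent on circle clustering, so a plain test would treat women in the same circle as independent. And Table 4 lists don't-know rows within several scales without saying whether they enter the test.

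At stake are power against a consistent shift, and the usefulness of these items for generating hypotheses, which needs size and precision.

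**Working it through.** **1. Which items are ordered.** Table 4 has 14 blocks.

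- Four ordered levels (five blocks): feelings about midwife care at 35 weeks, the same at 3 months, preparedness, managing in labour, and confidence (which also has a don't-know row).
- Three ordered levels plus don't know (three blocks): number of midwives, satisfaction with being known and remembered, and cultural or language sensitivity.
- No clean order (six blocks): caesarean type, place of birth, immunisation, choice of birthplace, involvement in decisions, and help and advice. The last two split the "no" answers by whether the woman wanted the thing.

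So 5 + 3 = 8 of 14 blocks are plainly ordered.

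**2. The plan's own figures.** The SAP gives no power, effect size or answer distribution for any categorical outcome, so there is none to reproduce. The only related design figure is 866 per arm for the primary outcome (section 4.1.1). With 69% against 77%, 90% power, a two-sided 5% level and 10% drop-out, the intervention-arm design effect is 1 + (8 × (1 + 1/8) − 1) × 0.05 = 1.40. Standard variants then give 843 to 862 per arm, within 3% of 866.

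**3. Power of an unordered against an ordered test.** Assumptions: the unnamed test is a Pearson chi-square on k levels (k − 1 df); effects follow proportional odds; clustering is ignored in both tests; and both have the same non-centrality λ. For a 1-df ordered test with power P, λ = (1.960 + z_P)². The chi-square's power is the probability that a non-central chi-square with k − 1 df and the same λ exceeds its 5% critical value (5.991 for 2 df, 7.815 for 3 df, 9.488 for 4 df).

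Worked case at P = 80%: λ = (1.960 + 0.842)² = 7.85. Power is 70.9% with 2 df, 64.5% with 3 df and 59.5% with 4 df. The losses are 9.1, 15.5 and 20.5 points.

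| Ordered-test power | λ | Loss, 3 levels | Loss, 4 levels | Loss, 5 levels |
|---|---|---|---|---|
| 50% | 3.84 | 9.9 | 15.5 | 19.2 |
| 60% | 4.90 | 10.5 | 16.8 | 21.1 |
| 70% | 6.17 | 10.3 | 16.9 | 21.8 |
| 80% | 7.85 | 9.1 | 15.5 | 20.5 |
| 90% | 10.51 | 6.5 | 11.6 | 16.0 |
| 95% | 13.00 | 4.2 | 7.9 | 11.3 |

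The five-level column applies if don't know is counted as a fifth level of a four-level scale. On the same logic, a three-level scale with don't know counted as a level moves to the four-level column.

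**4. Simulation check.** This used 20,000 tables per scenario, proportional odds, no clustering, and assumed sample sizes and distributions. Four levels at 40/40/15/5%, 500 per arm and odds ratio 1.4 gave 65.2% for the chi-square against 80.9% for the rank test, a loss of 15.7 points. With 780 per arm and odds ratio 1.5 it was 95.9% against 98.8%, a loss of 2.9 points. The loss shrinks as power rises.

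**5. Clustering, as an illustration.** Suppose the ICC of 0.05 and mean circle size of 8 assumed for the primary outcome also held here. The average variance inflation over the two arms would be (1.40 + 1)/2 = 1.20. A 3-df test that ignored it would have a true level of P(χ²₃ > 7.815/1.20 = 6.51), about 9% instead of 5%. The SAP gives no ICC for these items.

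**The case against.** Several points on the other side are sound and limit this finding.

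- **The test is unnamed.** A reader might infer that the SAP has chosen a test that ignores order. It does not say so, and a rank or trend test would also be an unadjusted between-group test. What stands is that the test is unspecified and order is not mentioned.
- **The power loss is not a property of the plan.** It depends on the test, proportional odds, the number of levels and the unknown power. No single range covers all the items, and for a non-monotone effect the loss can shrink or reverse.
- **Direction is not hidden.** A reader might infer that a significant p-value would leave the better arm unknown. Table 4 shows every category's percentage in each arm, so direction and raw size can be read off. Only the summary effect and its interval are missing.
- **The trial objective is not undermined.** The main satisfaction measure, the Friends and Family test, is a secondary outcome with a mean difference and 95% CI. The Table 4 items are additional outcomes.
- **Other sections do not strictly contradict 5.9.** It is tempting to cite section 5.16.1, "Missing values of categorical variables with three or more ordered categories will be modelled using ordinal logistic regression". That text concerns imputation for the primary-outcome sensitivity analysis and does not bind the analysis of other outcomes. Likewise "all confidence intervals will be presented at the 95% level" sets the level of any interval presented and does not require one for each outcome. Adjustment of additional outcomes is promised only where possible.

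The clustering statement in section 5.5 carries no such qualifier, and the categorical plan does not take it up.

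**Conclusion.** The concern holds as a modest, inexpensive improvement. For eight of the 14 Table 4 blocks, the plan names no test, makes no stated use of the order, gives no effect with an interval, does not say how circle clustering enters, and has no rule for don't-know answers. All of this can be read from sections 3.4, 5.5, 5.9 and 8.4.

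The size is conditional. With an unordered chi-square and proportional odds, the loss is about 12 to 17 points for four-level items where an ordered test would have about 50 to 90% power, and about 6.5 to 10.5 points for three-level items. It is smaller at higher power: 7.9 points for four levels at 95%, and about 3 in the strongest simulated case cited. It is larger if don't know counts as a level.

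The documents do not support reading this as a threat to the primary or secondary conclusions. These outcomes are hypothesis-generating and the trial was not sized on them.

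**What to change.** Split the categorical outcomes in section 5.9.

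- **Ordered items** (feelings about midwife care at both time points, number of midwives, satisfaction with being known and remembered, cultural sensitivity, preparedness, managing in labour, confidence): fit a proportional-odds model with English level as a fixed effect, a site effect, and circle effects in the intervention arm. Report the common odds ratio with 95% CI in a new Table 4 column. Label it conditional, because section 5.9 moves to marginal effects for the binary outcomes. Tabulate don't know and missing, but leave them out of the model.
- **Items without a clean order** (place of birth, caesarean type, choice of birthplace, involvement, help and advice, immunisation): keep an unordered test, and name it.
- **Non-convergence:** use the category-collapsing and model-simplification steps already in section 5.9.

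While editing, check the block on being known and remembered. Table 4 pairs the question from one section 3.4 item with the answer options of another.

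The cost is a few sentences, one table column and some extra model fitting, possibly with sparse extreme categories. The added assumption is proportional odds, which readers can judge from the percentages that remain in the table.

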5.10 Missing Data

For the analysis of the primary and secondary outcomes we assume that the data are missing completely at random. Sensitivity analysis to this assumption will be explored in sensitivity analyses for the primary outcome using multiple imputation (6). Further details are provided in the sensitivity analysis section. Moreover, we will only consider the primary outcome for women in the situation where all of its components are non-missing (i.e. available complete-case analysis).

The primary outcome is comprised of routine birthing data. The study team's commitment to attempt to locate and follow-up women with missing data has contributed to decrease this proportion as much as possible.

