4.1 Sample size

4.1.1 Sample size calculation (pre covid)

For the primary outcome ("Healthy baby"), in order to detect a difference in babies born "healthy" of 8% between the control and intervention arm, with 90% power and a 5% significance level, we would require at least 866 women per arm (i.e. 1732 total). This calculation also assumed an outcome proportion of 69% in the control arm, accounts for clustering within the intervention arm with an intra-cluster correlation (ICC) of 0.05 (in the intervention arm), mean group sizes of 8 with cluster size variability assuming Poisson distribution and assumes 10% drop-out in both arms. This sample size provides 84.8% power to detect a difference between arms of 7.3% in our, former primary outcome, spontaneous vaginal birth. Thus, a sample size 1732 is sufficiently powered to detect changes in both the primary outcome and SVD (now a secondary outcome).

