5.4 Withdrawals and loss to follow up

Women who choose to discontinue the group care will remain in the trial receiving standard of care and will be included in all analyses under the intention to treat principle. However, if a woman wishes to fully withdraw from the study the decision will be recorded, the withdrawal will be tabulated, and no further data will be collected. Moreover, women who withdraw before delivery will be excluded from the main analyses. However, we will still analyse their baseline data if available as stated in the protocol.

Women who have not been recorded as fully withdrawn and for whom no routine birth data is available are followed up with the Trusts by the trial team to seek their data. If unsuccessful, the participant is considered lost to follow up.

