5.16 Sensitivity analyses

5.16.1 Imputation analyses assessing the uncertainty around the primary outcome analysis estimate

To assess the extent to which study results are affected by missing data, a sensitivity analysis will be performed on imputed data for primary clinical outcome and stratification variables plus baseline characteristics: age, ethnicity, main language and educational level (2). The proportion of missing values for each variable will be assessed using numerical summaries. Univariable associations between missing values of each variable and observed values of other variables will be examined to understand how reliably a missing value might be imputed (3). This will be performed by constructing separate logistic regression models after creating a binary indicator variable for each variable with missing values coded as "1" and non-missing values coded as "0". The most applicable missing data mechanism will be informed by clinical knowledge of independent and dependent variables, reasons for missingness, and relationships between missingness and the observed values of collected variables.

Multivariate Imputation using Chained Equations (MICE) will be used to impute missing data under the expectation that both independent and dependent variables will have missing values and the data will not be monotonic missing (4). MICE replaces missing values with a random sample of plausible, imputed values drawn from their predictive distribution (5). First, an 'imputation' step will be performed, which involves constructing an imputation model that replaces missing data with one set of plausible values. Assuming that missing data are 'Missing At Random', the imputation model will specify a conditional distribution for missing values of each variable given the observed values of other variables. This imputation model will repeatedly replace missing values with a random sample of plausible values, creating a completed dataset with each imputation. The number of imputations (and thus completed datasets generated) will mirror the proportion of participants with at least one

missing value. For example, 25 complete datasets will be generated if 25% of study participants have at least one missing value (6).

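### No departure from 'missing at random' is pre-specified for the primary outcome, so the planned imputation says little about outcome-related missingness that differs by arm

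*SAP*

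**What the plan says.** Section 5.5 makes all main analyses complete-case, and 5.10 states MCAR as the assumption. Section 5.10 continues: "Sensitivity analysis to this assumption will be explored in sensitivity analyses for the primary outcome using multiple imputation (6".

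Section 5.16.1 describes that analysis as chained equations: "Assuming that missing data are 'Missing At Random', the imputation model will specify a conditional distribution". The variables it names are the primary outcome, the stratification variables, age, ethnicity, main language and education. It adds that auxiliary variables will be used but names none, and it does not list trial arm. It also says the likely missing-data mechanism will be considered, but attaches no analysis to a conclusion that data are not missing at random. Table 11 sets the complete-case result beside the imputed one.

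Outcomes go missing by three routes:
- Under 5.4, birth data that the Trusts cannot supply are chased. "If unsuccessful, the participant is considered lost to follow up".
- Also under 5.4, women who withdraw fully before delivery are left out of the main analyses.
- Under 3.2, the composite is missing if any component is missing, unless the baby is known not to have survived.

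**The concern.** Section 5.16.1 exists to show how far missing data affect the results. MAR imputation fills a missing outcome with what was seen in similar women. If the outcome is the main thing missing and the predictors are weak, the imputed result must land close to the complete-case result. Agreement between the two columns of Table 11 would then look reassuring whether or not the missing babies were less healthy in one arm.

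Such missingness is conceivable here. Women and maternity staff know the allocation (4.3), so full withdrawal could differ by arm. Under 3.2, a live baby already known to be preterm or admitted, but lacking another component, is set to missing although it cannot meet the definition of healthy. At stake is whether a reader can judge how much a modest positive result depends on the untraced records.

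**Working it through.** **Inputs (SAP 4.1.1, 4.1.2, 5.5).** The design difference is "of 8% between the control and intervention arm, with 90% power and a 5% significance level". Section 5.5 adds "all p-values will be two-sided". "This calculation also assumed an outcome proportion of 69% in the control arm", so 77% is implied under intervention. The calculation "accounts for clustering within the intervention arm with an intra-cluster correlation (ICC) of 0.05" in that arm, with "mean group sizes of 8 with cluster size variability assuming Poisson distribution and assumes 10% drop-out in both arms".

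**Reproducing the plan's figure.** Two proportions, 69% v 77%, two-sided 5%, 90% power: 646 per arm. With Poisson cluster sizes of mean 8, the design effect in the circle arm is 1 + ((1 + 1/8) × 8 − 1) × 0.05 = 1.40, so the mean over both arms is 1.20. Then 646 × 1.20 / 0.9 = 861 per arm, against the stated 866. The inputs are understood correctly.

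**Standard error for the primary analysis set.** 2190 − 298 = 1892 women, 946 per arm. With 10% missing, 946 × 0.9 = 851.4 per arm.
SE = √(0.69 × 0.31 / 851.4 + 1.40 × 0.77 × 0.23 / 851.4) = 2.33 points. The significance threshold is 1.96 × 2.33 = 4.6 points.

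**Bias.** In an arm with share m missing, the full rate is (1 − m) × observed rate + m × missing rate. Complete-case analysis therefore overstates that arm by m × (observed rate − missing rate). With the gap in the intervention arm only:

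| Share missing | 20-point gap | 30-point gap |
|---|---|---|
| 2% | 0.4 points | 0.6 points |
| 5% | 1.0 points | 1.5 points |
| 10% | 2.0 points | 3.0 points |

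**Tipping gap** = (observed difference − 1.96 × SE) / m, holding SE at 2.33:

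| Share missing | Observed 5 points | Observed 8 points |
|---|---|---|
| 2% | 22 | cannot be reached |
| 5% | 9 | 69 |
| 10% | 4.4 | 34 |

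An observed 5-point difference implies 74% rather than 77% in the circle arm. That makes SE 2.38 and the tipping gap at 10% missing (5 − 1.96 × 2.38) / 0.10 = 3.3 points. Hence about 3 to 4 points.

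**Does MAR imputation detect this?** A simulation had no true effect, a 69% healthy rate, control outcomes missing at random, and intervention outcomes missing more often when the baby was unhealthy. It imputed from arm and one weak baseline predictor, in large samples without clustering. Estimated difference in points (truth about 0):

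| Missing, gap | Complete case | MAR imputation |
|---|---|---|
| 5%, 15 points | +0.73 | +0.71 |
| 5%, 30 points | +1.36 | +1.33 |
| 10%, 15 points | +1.44 | +1.43 |
| 10%, 30 points | +3.07 | +3.00 |

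A separate run at 10% and 30 points added a strong, fully observed auxiliary (the outcome plus noise of SD 0.5). Complete case gave +2.84 and imputation +1.26: less than half the bias remained, but it did not vanish.

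**If arm is left out of the imputation model.** Imputed outcomes then carry no arm difference. At 10% missing, an observed 8 points becomes about 0.9 × 8 + 0.1 × 0 = 7.2, a pull towards zero that has nothing to do with the missingness mechanism.

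**The case against.** The strongest reply is that the plan does what 5.10 promises. MAR imputation relaxes MCAR, and MCAR is the assumption 5.10 says it will test. That stands: 5.10 is not wrong in itself, and the shortfall is against the broader aim in 5.16.1.

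A reader might go further and infer that the imputation must always return the complete-case answer, so that the plan cannot show anything about missing records. The documents do not support that. Section 5.16.1 commits to auxiliaries strongly related to the outcome or its missingness. When only one component is missing, the recorded components are natural candidates, and the simulation shows that strong auxiliaries remove much of the bias. They do not help when the whole birth record is missing, because they are missing with it.

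Nor should the open-label design be read as biased outcome extraction. Section 4.3 blinds those who supply or abstract the outcome data; only withdrawal and tracing remain exposed. Section 3.2 keeps known losses as not healthy. Section 5.8 lists relocation as a potential intercurrent event but does not say that it causes missing outcomes or differs by arm.

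Finally, 10% is the planning drop-out, not an observed share. The outcome comes from routine records that are actively chased, so the share could be far lower. At 2% missing the issue is small, and an 8-point effect is robust even at 10%. This limits the weight of the point but leaves the gap in the plan.

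**Conclusion.** The point holds in a limited form. The SAP specifies no analysis of the primary outcome that departs from MAR. The one part of 5.16 that varies assumptions about missing values, 5.16.6, concerns session counts in the dose-response model. With the named baseline predictors, the imputed and complete-case estimates will nearly coincide (within 0.1 point in the simulation), so their agreement would be weak evidence against outcome-related missingness that differs by arm.

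A result near the planned 8 points would be safe against any but an extreme gap. A result near 5 points would be fragile at 10% missing and considerably less so at 2%. These figures assume a gap in one arm only, the SAP's planning rates, ICC and cluster size, and a normal approximation. The true missing share and any gap are unknown. A change is advisable, but the primary analysis is not invalid without it.

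**What to change.** In 5.16.1:
- State that trial arm is in the imputation model, and name the auxiliary variables.
- Add a delta-adjusted (tipping-point) analysis of the healthy baby outcome. Shift the imputation model on the log-odds scale, separately by arm, over a grid fixed before unblinding, and re-draw the missing outcomes at each grid point.
- Report the risk difference and odds ratio with confidence intervals over the grid, and the smallest shift that changes the conclusion. Show MAR as the zero-shift point in Table 11.

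The log-odds scale matters because adding 30 points to a rate of 77% would exceed 100%. For orientation, a fall from 77% to 57% is a shift of 1.21 − 0.28 = 0.93, and a fall from 77% to 43% is 1.21 + 0.28 = 1.49. A grid from about −1.5 to +1.5 would therefore cover the tipping gap for the planned effect at 10% missing.

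The cost is SAP wording, one extra table and modest computing. It needs no new data, but it is more than a loop over existing imputed datasets: outcomes must be re-drawn, and 5.9 takes confidence intervals from a bootstrap. Extending the analysis to spontaneous vaginal delivery is optional, since 5.10 promises the check only for the primary outcome and 3.3 gives that outcome a second data source.
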